The studies described above are observational and so far no randomized clinical trial has been published evaluating the efficacy of NIFC to improve the identification of the extra-hepatic biliary structures. Additionally it would be relevant to investigate the ability of the NIFC to reduce intraoperative bleeding, duration of laparoscopic cholecystectomy. Further, it is central to assess whether NIFC can improve the outcomes in some subpopulation of patients for whom the evaluation and dissection of the Calot's triangle is difficult, e.g. obese patients or patients undergoing inflammatory processes. Finally, the potential use of NIFC as a training tool in laparoscopic surgery is still to be studied.

c. Strengths and Limitations

The strength of the study is the ability to investigate whether the extra-hepatic biliary tract is more visible using NIFC when compared with white light (WLI) alone. It is a multicenter study with diverse patient populations and surgeons from different countries/continents that will validate this method globally.

Limitations may include impossibility to randomize by surgeon.

3. Study Overview

The Study is designed to compare the effectiveness of Near Infrared Fluorescence Cholangiography (NIFC) to standard white light imaging (WLI) in visualizing and identifying the main biliary and hepatic structures (Cystic Duct, Right Hepatic Duct, Common Hepatic Duct, Common Bile Duct, Cystic-CBD junction, Cystic-Gallbladder junction and any Accessory Ducts) during laparoscopic cholecystectomy.

4. Study Objectives

a. Primary Objective:

Multi-center Study Protocol: Efficacy of Near Infrared Incisionless Fluorescent Cholangiography (NIFC) during Laparoscopic Cholecystectomy

Demonstrate that NIFC performs better than standard white light (WLI) alone in visualizing and identifying extra-hepatobiliary structures (Cystic Duct, Right Hepatic Duct, Common Hepatic Duct, Common Bile Duct, Cystic-CBD junction, Cystic-Gallbladder junction, and any Accessory Ducts) before and after dissection during Laparoscopic Cholecystectomy (LC).

b. Secondary Objectives:

1. Demonstrate that NIFC is an effective teaching tool to assist students and residents present in the O.R. during the procedure to identify extra-hepatobiliary structures (before/after dissection).
2. Demonstrate that the Time to Clip, which is defined as the time from the moment Calot's Triangle is first visualized to when the clip is applied, is reduced when using NIFC vs WLI alone.

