Upon entry in the clinical trial, the master study database (REDCap, described later in Section 16) will randomly allocated patients to one of the study arms (1:1) within site (1:1) using a computer generated random sequence. This will provide an allocation sequence for each site. Once a patient is enrolled and a database file in REDCap is initiated for that patient, he/she will be assigned electronically to one of the study arms.

Patient will be blind to the intervention but surgeon blinding will not be feasible due to the nature of the intervention. The study will involve a considerable number of surgeons in each site, which should compensate any potential bias of some of them in favor or against either approach.

e. Flow chart

Multi-center Study Protocol: Efficacy of Near Infrared Incisionless Fluorescent Cholangiography (NIFC) during Laparoscopic Cholecystectomy

[figure not shown]
Figure 1 shows the flow chart for the study, a multi-centered randomized controlled trial (RCT) 1:1 with two arms:

1. Control: WLI

A laparoscopic cholecystectomy will be performed using Xenon white light imaging (WLI) only.

2. Experimental: NIFC

A laparoscopic cholecystectomy will be performed using both white light imaging and near infrared light imaging with indocyanine green (ICG) intravenous dye.

9. Data collection and procedures

Data will be collected before, during and at the end of surgery; and one week after surgery.

a. Pre-Op data collection

i. Patient data

- Age
- Gender
- Weight
- Height
- BMI

ii. Patient clinical characteristics

- Liver disease
- Lithiasis
- Surgical status: elective/urgent/emergent

b. Intra-Op data collection

i. For NIFC arm only

- Time of ICC administration
- Was there any Adverse Reaction? If so, what happened and how was the patient treated?

ii. For both arms: PRIOR to dissection

- Categorize initial visualization
 - Amount of fat
 - Amount of inflammation
 - Presence of adhesions / scar tissue
- Remove the fat from the Calot's triangle area, retract the gallbladder and Hartmann's pouch
- Surgeon/Observer documents which extra-hepatic biliary structures are identified without doubt
- Start Dissection. Document the time hilar dissection was begun (baseline time)

iii. For both arms: AFTER dissection

- Surgeon/Observer documents which extra-hepatic biliary structures are identified without doubt
- Time to Clip: Document the time the Cystic Duct was clipped
- Volume of Bleeding
- Incidence of Bile Leakage

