c. Patient Randomization

Each surgeon will follow the standard laparoscopic surgical protocol of his/her center, and will comply with the following additional steps according to which arm of the study the patient is assigned:

i. Control arm (WLI only) procedures

1. After inserting the scope in the abdominal cavity, once other standard operatory procedures (e.g., taking down adhesions if necessary, or releasing scar tissue) are completed using white light imaging (WLI) only, the Researcher will record the time when Calot's triangle is first visualized. From this moment on, the surgery will be recorded.
2. After removing the fat from the gallbladder area, lifting the gallbladder over the liver, and grabbing the Hartman's pouch to visualize the Calot's triangle, but PRIOR TO DISSECTION, the Researcher will determine what extra-hepatic biliary structures can be specifically identified. Of note: because one of the goals of the Study is to evaluate NIFC as a teaching tool, residents and juniors should record what structures they were able to identify by themselves before any intervention of the attendant surgeon.
3. Then, AFTER DISSECTION, a similar assessment of what extra-hepatic biliary structures can be specifically identified using WLI only will be performed.
4. Anatomic anomalies of the biliary system will be documented on the case form and if an anatomic variation is found, a snap shot photo will be taken in addition to the video.
5. Immediately before clipping or proceeding with open surgery, the total time from Step 1 will be recorded, known herein as the "Time to Clip";

6. Before leaving the operation room, all participant surgeons and observers will complete the Intra-Operative Case Report Form (Appendices D and E, respectively).

ii. Experimental arm (NIFC) procedures

1. Patient randomized to the experimental arm, at least 45 mins before surgery, will receive a weight-scaled dose of indocyanine green (0.05 mg/kg) by IV and the time of administration and any adverse reactions will be recorded.
2. After inserting the scope in the abdominal cavity, once other standard operatory procedures (e.g., taking down adhesions if necessary, or releasing scar tissue) are completed using white light imaging (WLI) only, the Researcher will record the time when the Calot's triangle is first visualized. From this moment on, the surgery will be recorded.

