3. After removing the fat from the gallbladder area, lifting the gallbladder over the liver, and grabbing the Hartman's pouch to visualize the Calot's triangle, but PRIOR TO DISSECTION, the Researcher will use NIFC to determine what extra-hepatic biliary structures can be specifically identified. This involves toggling the light source back and forth between STD mode (WLI) and ICG mode (NIFC). Of note: because one of the goals of the Study is to evaluate NIFC as a teaching tool, residents and juniors should record what structures they were able to identify by themselves before any intervention of the attendant surgeon.
4. Then, AFTER DISSECTION, a similar assessment of what extra-hepatic biliary structures can be specifically identified using NIFC will be performed.
5. Anatomic anomalies of the biliary system will be documented on the case form and if an anatomic variation is found, a snap shot photo will be taken in addition to the video.
6. Immediately before clipping or proceeding with open surgery, the total time from Step 1 will be recorded, known herein as the "Time to Clip";
7. Before leaving the operation room, all participant surgeons and observers will complete the Intra-Operative Case Report Form (Appendices D and E, respectively).

d. Post-Operative Case Report Form

During the standard follow-up exam, typically 7-10 day post-op, the Researcher will complete the Post-Operative Case Report Form (Appendix F).

e. Bile Duct Injury Form (if needed)

If the procedure results in a bile duct injury, the operating surgeon will complete the ancillary Bile Duct Injury Form (Appendix G).

13. Statistical Plan

a. Sample size

We estimate that the six participant centers will be able to enroll a minimum of 1000 patients in a 12 months period. Table XX shows the minimum effect size (increase in the rate of detection) that we will be able to detect with a 90% power or more, 5% level of significance, one-side test, when the detection rate in the control group are the ones indicated in the first column.

Structure	Before dissection		After dissection	
	DR control group	DR increase (effect size)	DR control group	DR increase (effect size)
Cystic	50%	10%	100%	--
Right Hepatic Duct	40%	10%	80%	7%
Common Hepatic Duct	46%	10%	70%	8%
Common Bile Duct	46%	10%	96%	3%
Cystic-CBD junction	29%	9%	60%	9%
Cystic-Gallbladder junction	60%	9%	70%	8%
Accessory Ducts	1%	3%	2%	4%

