3. AFTER-DISSECTION

A. Document visualization of extra-hepatic biliary anatomy:

For both arms, scope the Calot's triangle area using STD (white-light) mode. If in the NIFC arm, toggle between STD and ICG modes on light source as needed. Check the appropriate boxes below based on what is visible:

	Yes	Maybe	No
Cystic Duct			
Right Hepatic Duct			
Common Hepatic Duct			
Common Bile Duct (CBD)			
Cystic-CBD junction			
Cystic-Gallbladder junction			
Accessory Ducts			

B. For NIFC Arm Only: "Reflux Maneuver" Attempted? Yes No

Repeat the Reflux Maneuver. Check the appropriate boxes based on what is visible:

	Yes	Maybe	No
Cystic Duct			
Cystic-CBD junction			
Cystic-Gallbladder junction			

4. Time to Clip: Time the Cystic Duct was clipped: _____ AM / PM

5. Volume of Bleeding: _____ mL in the bucket/bag or from anesthesia chart at the conclusion of the procedure

6. Bile Leakage: No Yes If yes, Liver bed Other: _____ Did NIFC help identify leak? Yes No

7. Anatomic Anomalies: No Yes If yes, describe: _____

If yes, do you feel NIFC helped you identify this anomaly? Yes No N/A (WLI arm)

8. Was IOC performed? Yes No

9. Were CBD Stones present? Yes No Not Checked

10. Was the procedure converted to Open? Yes No

If yes, explain why: _____

11. Was there a Bile Duct Injury (BDI) during the surgery? Yes No

If yes, complete the BDI Form as described in the Study Protocol.

12. SURGEON FEEDBACK after NIFC:

Did you feel NIFC made your procedure SAFER? Yes No

Were you more CONFIDENT using NIFC vs WLI alone? Yes No

Would you PREFER to use NIFC again vs WLI alone? Yes No

e. Intra-Op Case Report Form – Observer

Near Infrared Incisionless Fluorescent Cholangiography (NIFC)

INTRA-OPERATIVE CASE REPORT FORM - OBSERVER

INSTITUTION: _____

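### Time to Clip has four different starts and two different stops, and it includes an after-dissection study assessment that may take unequal time in the two arms

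*Combined protocol and SAP*

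**What the plan says.** **Start of the clock.**
- Section 4.b, objective 2, defines Time to Clip as the endpoint "which is defined as the time from the moment Calot's Triangle is first visualized to when the clip is applied".
- Section 12.c.i (control), step 1, agrees: "the Researcher will record the time when Calot's triangle is first visualized". The same event is step 2 of the NIFC list in 12.c.ii.
- Section 9.b.ii, for both arms: "Start Dissection. Document the time hilar dissection was begun (baseline time").
- The surgeon form (Appendix d) has a time of initial visualization at item 2.C, after fat removal and retraction at 2.B. It has a separate time for hilar dissection.
- Both lists in section 12.c say: "Immediately before clipping or proceeding with open surgery, the total time from Step 1 will be recorded". In the NIFC list, step 1 is: "Patient randomized to the experimental arm, at least 45 mins before surgery, will receive a weight-scaled dose of indocyanine green".

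**Stop of the clock.** Section 12.c stops just before clipping or before going on to open surgery. Section 9.b.iii and item 4 of the surgeon form record the time the cystic duct was clipped.

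**What happens before the stop.** After dissection the NIFC list says that "a similar assessment of what extra-hepatic biliary structures can be specifically identified using NIFC will be performed" (step 4). The control list has a white-light counterpart (step 3). On the surgeon form, item 3.A is the structure grid, with toggling to ICG mode as needed in the NIFC arm. Item 3.B, NIFC only, asks whether the maneuver was attempted and then says: "Repeat the Reflux Maneuver. Check the appropriate boxes based on what is visible". Time to Clip is item 4.

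**Analysis.** Section 13.b compares time to clipping by Kruskal-Wallis. Nothing in the plan times, pauses for or deducts the assessments.

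**The concern.** Objective 2 is directional: it sets out to demonstrate that the time "is first visualized to when the clip is applied, is reduced when using NIFC vs WLI alone". Such a claim needs one interval, measured in the same way in both arms and at every site. Here two sites could follow the text and record different intervals, and a literal reading of the NIFC list gives that arm a different origin from the control arm.

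The second issue is what the interval contains. A structure assessment made after dissection cannot shorten the dissection. If it takes longer in one arm for study reasons, that time enters the comparison as if it were operating time. The form collects no times from which the size of this component could be judged.

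**Working it through.** The plan states no SD, expected saving, sidedness or power for Time to Clip, so there is no figure of its own to reproduce. The check has two parts.

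**1. Order of events**

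| Event | Control, 12.c.i | NIFC, 12.c.ii | Surgeon form |
|---|---|---|---|
| ICG injection | none | step 1 | item 1 |
| First view of Calot's triangle | step 1 | step 2 | no separate field |
| Fat removal, retraction | step 2 | step 3 | 2.B |
| Pre-dissection assessment | step 2 | step 3 | 2.C (start time here), 2.D |
| Hilar dissection starts | no separate step | no separate step | timed |
| After-dissection assessment | step 3 | step 4 | 3.A, 3.B |
| Time to Clip | step 5 | step 6 | item 4 |

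Three things follow.
- The starts are different events. The start in 9.b.ii leaves out fat removal and the pre-dissection assessment in both arms. The form's start leaves out fat removal.
- Counting from step 1 means the Calot's-triangle view in the control arm, but the injection, at least 45 min before surgery, in the NIFC arm.
- The after-dissection assessment comes after all four starts and before both stops, so it is always counted, in both arms. Section 13.b also refers to identification before clipping.

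**2. Scale, as an illustration only**

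Inputs:
- 500 per arm (section 13.a).
- SD 17.43 min, the whole-operation SD of a 43-patient study cited in section 2.b; using it for Time to Clip is an assumption.
- True saving of 3 min (assumption).
- Extra NIFC assessment time b of 0, 0.71 or 1.9 min. The last two are total NIFC times from two studies cited in section 2.b; using them as the difference between arms is an assumption.
- Two-sided 5% test, normal approximation for a difference in means.

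SE = 17.43 × √(2/500) = 1.102 min. Power = Φ((3 − b)/SE − 1.96).

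- b = 0: 3/1.102 − 1.96 = 0.76, power 78%.
- b = 0.71: 2.29/1.102 − 1.96 = 0.12, power 55%.
- b = 1.9: 1.10/1.102 − 1.96 = −0.96, power 17%.

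One-sided 5%: 86%, 67% and 26%.

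Sensitivity to SD (3-min saving, two-sided): SD 10 gives 99.7%, 95% and 41%; SD 25 gives 48%, 30% and 10%.

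Sensitivity to the saving (5 min, SD 17.43): 99.5%, 97% and 80%.

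The smallest saving detectable with 90% power at SD 17.43 is (1.96 + 1.28) × 1.102 = 3.57 min. An imbalance of one or two minutes would therefore matter for savings of a few minutes and much less for larger ones.

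**The case against.** A reader might infer that NIFC is necessarily charged with measurement time and that the comparison therefore hides a real saving. The documents do not support this, for five reasons.

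- No assessment duration is given for either arm. Both arms look for the same seven structures, toggling is as needed, and section 11.b describes a foot pedal for quick switching. A white-light search for poorly visible ducts could take as long or longer.
- The reflux maneuver is conditional. Section 7 allows it in some cases, item 2.D ties it to a cystic duct not seen with fluorescence, and the surgeon form asks whether it was attempted. The cited series report the cystic duct seen with NIFC in 52 of 52 patients, and in 93% before dissection, so it may seldom be needed.
- Section 12.c has the forms completed before leaving the operating room, so writing time need not fall before the clip.
- Section 11.b describes alternating modes before, during and after dissection as how the device is used. Some after-dissection ICG viewing is therefore intervention and not measurement, and subtracting it in the main analysis could favour NIFC.
- The two cited durations are total NIFC times, not increments over a white-light look. A net difference of zero is compatible with the documents.

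All of this stands, and it removes any claim about direction or size. A reader might also infer that the start in 9.b.ii biases the comparison by itself. It does not: applied to both arms it only drops the pre-dissection look, and section 9 never says that Time to Clip is computed from it.

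The objection does not remove the conflicting starts and stops, the faulty step reference, or the untimed assessment inside the interval.

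**Conclusion.** The point holds as a definition problem with a possible bias. Time to Clip has four candidate starts and two stops. Converted cases have a stop in section 12.c but no matching time field on the form. The after-dissection assessment is inside the interval in both arms under every reading, and only NIFC has added steps there. The sign and size of any net difference are unknown.

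The fall from 78% to 55% or 17% power shows only what an imbalance of 0.71 or 1.9 min would do under the assumed SD and a 3-min saving; it is not an estimate for this trial. At a 5-min saving the loss is small for 0.71 min (97%) and moderate for 1.9 min (80%).

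Read literally, the step 1 reference would add at least 45 min to the NIFC arm. Since objective 2 names Calot's triangle, this looks like a numbering slip, but it should not be left for sites to interpret. The endpoint is secondary, and the correction is worth making because it is cheap.

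**What to change.** 1. Use objective 2's start, the first view of Calot's triangle, in both arms. Delete the *baseline time* label in 9.b.ii and move the form's start time to match.
2. In 12.c.ii step 6, point to the Calot's-triangle step instead of step 1.
3. Choose one stop event for section 12.c, section 9.b.iii and the form, and state how Time to Clip is obtained for converted cases.
4. Record clock times for the end of dissection and the end of items 3.A/3.B in both arms, or read them from the video, which already runs from the first view of Calot's triangle.
5. In 13.b, keep total Time to Clip as defined in objective 2, and add a prespecified analysis that excludes the 3.A–3.B interval in both arms. Readers who regard the ICG look as part of the intervention, and those who regard it as measurement, then both have their answer.

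Cost: two extra clock times per patient, one extra analysis and a few sentences of text.

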h. Schedule of events	45
i. WMA Declaration of Helsinki - Ethical Principles for Medical Research Involving Human Subjects.....	46
i. Preamble.....	46
ii. General Principals	46
iii. Risks, Burdens and Benefits.....	47
iv. Vulnerable Groups and Individuals.....	48
v. Scientific Requirements and Research Protocols	48
vi. Research Ethics Committees	49
vii. Privacy and Confidentiality	49
viii. Informed Consent.....	49
ix. Use of Placebo.....	50
x. Post-Trial Provisions.....	51
xi. Research Registration and Publication and Dissemination of Results	51
xii. Unproven Interventions in Clinical Practice	51

1. Summary

Title:	Efficacy of Near Infrared Incisionless Fluorescent Cholangiography (NIFC) during Laparoscopic Cholecystectomy (LC)
Primary Objective:	Demonstrate that NIFC performs better than standard white light (WLI) alone in visualizing and identifying extra-hepatobiliary structures (Cystic Duct, Right Hepatic Duct, Common Hepatic Duct, Common Bile Duct, Cystic-CBD junction, Cystic-Gallbladder junction, and any Accessory Ducts) before and after dissection during Laparoscopic Cholecystectomy (LC).
Secondary Objectives:	
1. Demonstrate that NIFC is an effective teaching tool to assist students and residents present in the O.R. during the procedure to identify extra-hepatobiliary structures (before/after dissection).2. Demonstrate that the Time to Clip, which is defined as the time from the moment Calot's Triangle is first visualized to when the clip is applied, is reduced when using NIFC vs WLI alone.3. Compare the mean number of procedures that required Conversion to Open using NIFC vs WLI alone.4. Compare the mean Volume of Bleeding using NIFC vs WLI alone.5. Compare the Incidence rate of Bile Leakage from the liver bed using NIFC vs WLI alone.6. Compare the Incidence rate of Bile Duct Injury (BDI) using NIFC vs WLI alone.7. Compare the mean Surgeon Confidence Level using NIFC vs WLI alone.
Indication:	Laparoscopic Cholecystectomy (LC)
Investigational Design:	Two arms multi-center randomized controlled clinical trial with patients randomized by center.
Inclusion/exclusion criteria:	
Inclusion Criteria
 
1. Patients of both genders2. Minimum age: 18 years old3. Spoken and written command of the language spoken in the country's center

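### Time to Clip in the NIFC arm is counted from Step 1, which in that list is the ICG injection and not first view of Calot's triangle

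*Combined protocol and SAP*

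**What the plan says.** **Definition.** Secondary Objective 2 appears in Section 1 (Summary) and again in Section 4.b. It opens "Demonstrate that the Time to Clip, which is defined as the time from the moment" and, after naming Calot's, goes on "Triangle is first visualized to when the clip is applied". It makes no distinction between arms.

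**Control list (Section 12.c.i).** In Step 1 the researcher notes the time at which Calot's "triangle is first visualized. From this moment on, the surgery will be recorded". Step 5 then reads "the total time from Step 1 will be recorded, known herein as the" Time to Clip.

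**NIFC list (Section 12.c.ii).** Step 1 is a different event: "Patient randomized to the experimental arm, at least 45 mins before surgery, will receive a weight-scaled dose of indocyanine green". First view comes in Step 2, where the researcher must "record the time when the Calot" triangle is first seen, and video recording starts. Step 6 then defines Time to Clip with the wording of the control list: "Immediately before clipping or proceeding with open surgery, the total time from Step 1 will be recorded".

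**Other places.** Section 9.b.ii lists no first-view time and says "Document the time hilar dissection was begun (baseline time"). Section 9.b.iii asks for the time of cystic duct clipping. Section 13.b compares time to clipping between arms by Kruskal-Wallis, without naming a start or stop. The surgeon's intra-operative form collects clock times for ICG administration (item 1, NIFC only), initial visualization (2.C), hilar dissection, and clipping (item 4). It has no field for an elapsed time and no subtraction rule.

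**The concern.** The sentence that defines the measurement in the NIFC arm points to a different start event from the one in the objective and in the control arm. An interval compared between arms has to start at the same event in both. Here one arm would start at an injection that the other arm never receives, well before the operation begins. The error would work against NIFC, on an endpoint that the trial sets out to show is reduced with NIFC. Surgeons are not blinded (Section 8.d), so the start time should not be left to be chosen once results are visible.

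**Working it through.** The plan gives no expected value, SD or power for Time to Clip, so there is no figure to reproduce. The check is a comparison of the texts, followed by arithmetic on the offset.

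**1. Start and stop events side by side**

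| Place | Start | Stop |
|---|---|---|
| Sections 1 and 4.b, both arms | First view of Calot's triangle | Clip applied |
| 12.c.i Step 5, control | Step 1 = first view | Just before clipping or conversion |
| 12.c.ii Step 6, NIFC | Step 1 = ICG injection | Just before clipping or conversion |
| Section 13.b | Not stated | Clipping |
| Surgeon form | Several clock times, none designated | Cystic duct clipped |

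Only NIFC Step 6 conflicts with the defined start. The likely cause is that control-arm wording was carried over after an ICG step was put at the head of the NIFC list.

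**2. Size of the offset if Step 6 is followed literally**

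Let L be the time from injection to surgery (at least 45 min, NIFC Step 1), A the time from start of surgery to first view (not given, at least 0), and D the defined interval from first view to clip.

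- Control arm: recorded time = D.
- NIFC arm: recorded time = L + A + D.
- Offset, NIFC arm only = L + A ≥ 45 min.

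A true NIFC saving of 5, 10 or 20 min would show as an excess of at least 45 − 5 = 40, 45 − 10 = 35 or 45 − 20 = 25 min. For NIFC to look faster on average, the true mean saving would have to exceed 45 min. With Step 2 as the start, the offset is 0.

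**3. Effect on the planned test, same condition**

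Every literal NIFC time exceeds 45 min, so the estimated P(NIFC > control) is at least the share of control times under 45 min. With 500 per arm (the figure in Section 13.a), its standard error under the null is √(1001 / (12 × 500 × 500)) = 0.01827. The two-sided 5% cut-off is therefore 0.5 + 1.96 × 0.01827 = 0.5358.

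In the layout least favourable to a finding that NIFC is slower, all other control times lie above all NIFC times. There, 267 of 500 control times under 45 min gives p = 0.063, and 268 of 500 (0.536) gives p = 0.049. From 268 upwards the test would declare NIFC slower whatever the true effect. The documents do not give this share, so the calculation shows that a reversal is possible and says nothing about how probable it is.

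**4. Can the form supply the defined interval?**

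Only in part. On the surgeon's form, fat removal is item 2.B and Time of Initial Visualization is in 2.C. In Section 12, first view is recorded before the step that removes fat. Completed in order, the form may therefore give a time later than the defined start. Item 2.A also refers to initial visualization and precedes fat removal, so the field is open to two readings. The video starts at first view in both arms and does not have this problem.

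**The case against.** The best reply is that this is a cross-reference slip with little reach. The endpoint is defined twice, identically for both arms. NIFC Step 2 itself orders the first-view time to be recorded and starts the video there. The form has nowhere to enter a total counted from Step 1, so the error reaches the data only if someone subtracts the ICG time against the stated definition. The endpoint is secondary, and the test calculation depends on literal use of Step 6 and on an unknown share. All of this stands, and it limits the practical risk. It does not remove the contradiction: the step that names the endpoint in one arm gives the wrong start, and Section 13.b does not settle which times to use.

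A reader might go further in three ways that the documents do not support:

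- That NIFC times will in fact be measured from the injection. Nothing shows this, and the form's structure makes it unlikely.
- That the label on hilar dissection in Section 9.b sets up a competing start. It is never said to be the start of Time to Clip, so it needs clarification only.
- That the stop rules bias the comparison. The mention of open surgery in Section 12 may simply extend the rule to cases without a laparoscopic clip, and Section 13.b expects very few conversions. No size can be put on it.

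The opposite inference also fails. It is tempting to say that the form already yields the defined interval in both arms and needs no change, but the order of 2.B and 2.C does not allow that.

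**Conclusion.** The point holds and should be fixed. As written, NIFC Step 6 contradicts the definition in Sections 1 and 4.b and the matching step in the control list. The size is an offset of at least 45 min in the NIFC arm alone, which could reverse the comparison in Secondary Objective 2. That figure assumes that Step 6 is applied literally and that ICG is given with the lead time stated in NIFC Step 1; it needs no assumption about variability. The probability of literal use is not known and is probably low. The primary detection rates are not affected. The order of items on the form, the label in Section 9.b and the stop for converted cases are matters to reconcile, with no size claimed.

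**What to change.** - **Section 12.c.ii, Step 6:** replace the reference to Step 1 with Step 2.
- **Section 13.b:** state that Time to Clip in both arms runs from first view of Calot's triangle to clip, and name the source of each time.
- **Surgeon's form:** relabel Time of Initial Visualization as first view of Calot's triangle, or move it ahead of fat removal. If data are already collected, either take first view from the surgical video or use the same form field in both arms and say so.
- **Section 9.b:** list the first-view time, and make clear that the hilar dissection time is not the start of Time to Clip.
- **Converted cases:** reconcile the stop in Sections 1 and 4.b and on the form with that in Section 12, before analysis.

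The cost is a few words in the protocol, plus a small label change on the form or some video checking. No extra patients, procedures or change of test are needed.
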